7.2.2 Local Skin Reactions Assessments

At every visit, LSRs will be assessed in the Treatment Area and adjacent surrounding skin using a four-point ordinal scale of 0 = absent, 1= mild (slight, barely perceptible), 2=moderate (distinct presence) and 3 = severe (marked, intense) for the following:

- Erythema
- Flaking/scaling
- Crusting
- Swelling/edema
- Vesiculation/pustulation
- Erosion/ulceration
- Hyperpigmentation
- Hypopigmentation
- Scarring

These LSRs will be collected independently of adverse events (AEs). Only LSRs that require medical intervention (e.g., prescription medication), require withholding of the application of the test article), or extend beyond 2 cm outside of the Treatment Area will be documented as AEs. Any LSRs that are not listed above will be recorded as AEs.

7.2.3 Fitzpatrick Skin Type Assessment, Brief Physical Exam and Vital Signs

Fitzpatrick skin type (I-VI) assessment will be performed at the Baseline Visit.

Fitzpatrick Skin Phototype		
Skin Phototype	Typical Features	Tanning Ability
I	Pale white skin, blue/Hazel eyes, blond/red hair	Always burns, does not tan
II	Fair skin, blue eyes	Burns easily, tans poorly
III	Darker white skin	Tans after initial burn
IV	Light brown skin	Burns minimally, tans easily
V	Brown skin	Rarely burns, tans darkly easily
VI	Dark brown or black skin	Never burns, always tans darkly

In addition, a brief physical examination will be performed at the Baseline Visit. The physical examination will include head and neck, cardiovascular, respiratory, gastrointestinal (abdomen), gross motor and gait with findings recorded in the medical history. Vital signs including temperature, blood pressure (diastolic and systolic), heart rate, and respiration rate, as well as height and weight, will be assessed at the Baseline Visit.

7.2.4 Laboratory Tests

Urine Pregnancy Tests (UPTs) will be performed on all WOCBP at the Baseline Visit prior to randomization and at the EOS visit.

7.2.5 Prior/Concomitant Medications and Concurrent Therapies/Procedures

Details of prior and concomitant medication use and concurrent therapies/procedures will be collected for each subject.

8 STATISTICAL METHODS

8.1 General Considerations

All statistical processing will be performed using SAS[®] Version 9.4 or higher, unless otherwise stated. For continuous variables, descriptive statistics will include the number of subjects with non-missing data (n), and mean, median, standard deviation, minimum and maximum values. For categorical variables, the number and percentage of subjects within each category will be presented. Subject data listings will be sorted by treatment group, study site and subject number. Summaries will be provided as specified below.

8.2 Analysis Populations

[figure not shown]
8.2.1 Safety Population

The Safety population will include all randomized subjects who received the test article.

[figure not shown]
8.2.2 mITT Population

The modified Intent-to-Treat (mITT) population will include all randomized subjects who applied at least one dose of test article.

8.2.3 PP Population

8.3 Methods for Handling Missing Data

8.4 Subject Disposition

Subjects who complete the three consecutive days of treatment and all of the Visit 6/Day 57 evaluations will be considered to have completed the study.

The number and percent of subjects who were enrolled in the study, who completed the study, and who withdrew from the study will be tabulated by treatment group for the Safety, mITT and PP populations along with their reasons for discontinuation.

Subjects who are excluded from the PP population with their reasons for exclusion will be listed.

The number of subjects who were screen failures will be tabulated by site and reason for screen failure.

8.5 Screening and Baseline Assessments

8.5.1 *Demographic and Baseline Characteristics*

Gender, age, race, ethnicity and Fitzpatrick Skin Phototype will be summarized by treatment group for the Safety, mITT and PP populations.

Characteristics of the AK lesions in the Treatment Area at Baseline will be summarized including the location, total number of AK lesions and the number of AK lesions at least 4 mm in diameter.

Informed consent information and subject eligibility status will be provided in a listing.

8.5.2 *Medical History and Physical Exam*

Medical/dermatological history will be coded into system organ class (SOC) and preferred term (PT) using the Medical Dictionary for Regulatory Activities (MedDRA) Coding Dictionary version 19.0. The number and percentage of unique subjects reporting each medical history will be summarized by SOC and PT for the Safety population. Start and end dates with ongoing status will be presented in a subject data listing. Abnormalities noted during the physical exam will be collected in the medical history.

8.5.3 *Vital Signs*

Systolic and diastolic blood pressures (mm Hg), pulse rate (beats/minute), temperature (°F), and respiration rate (breaths/minute), as well as, height (in) and weight (lbs) will be summarized by treatment group for the Safety population.

8.5.4 *Prior Medications/Therapies/Procedures Identified in the Exclusion Criteria*

Listings will be provided for the prior medications and therapies/procedures that needed a washout period prior to the subjects' enrollment.

8.6 Efficacy Analyses

8.6.1 *Primary Efficacy Analyses*

The primary efficacy endpoint is the proportion of subjects in the PP population with treatment success (complete clearance of AK lesions) at Day 57, where complete clearance of AK lesions is defined as having no (zero) clinically visible AK lesions in the Treatment Area.

Subjects who discontinued early from the study due to lack of treatment effect or who worsen and require alternate or supplemental therapy will be included in the PP and the mITT populations as treatment failures (non-responders). For subjects who are discontinued prematurely for any other reasons, LOCF imputation will be used to impute missing AK lesion counts in the mITT population.

Test for bioequivalence of test and reference treatments

To establish bioequivalence for the proportion of subjects with treatment success, the following hypotheses will be tested in the PP population:

$$H_0: \pi_T - \pi_R \leq -0.2 \text{ or } \pi_T - \pi_R \geq 0.2$$
$$H_A: -0.2 < \pi_T - \pi_R < 0.2$$

,where π_T is the proportion of subjects with treatment success in test treatment group (generic ingenol mebutate gel (Actavis)) and π_R is the proportion of subjects with treatment success in reference treatment group (Picato[®] gel).

The null hypothesis, H_0 , is rejected with a type I error (alpha) of 0.05 (two one-sided tests) if the estimated 90% Wald's confidence interval with Yate's continuity correction for the difference of the success rates between test and reference treatment groups ($\pi_T - \pi_R$) is contained within the interval [-0.2, 0.2]. Rejection of the null hypothesis supports the conclusion of equivalence of the test and reference treatments.

This analysis will be repeated for mITT population as a supportive analysis.

Test for superiority of each active treatment over vehicle treatment

To establish that the study is sufficiently sensitive to detect difference between treatments, two-sided, continuity-corrected chi-square tests with an alpha of 0.05 will be used to test the superiority of each active treatment group's treatment success rate over

that of the Vehicle treatment in the mITT population. If any cells have an expected frequency of less than 5, then Fisher's exact tests will be used instead.

This analysis will be repeated for PP population as a supportive analysis.

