Study Procedures	
The study will consist of six clinic visits (see Schedule of Events). Subjects can be screened up to 30 days prior to Baseline for those subjects that are qualified for enrollment, but require wash-out of prohibited medications and/or therapies. Screening and Baseline may be combined into a single visit for those subjects who do not require washout. Subjects who require washout for longer than 30 days will be re-consented.
 
Visit 1 (Screening/Baseline): Day 1. The study requirements and procedures will be reviewed and written informed consent must be obtained prior to the initiation of any study-related procedures. Demographics, inclusion/exclusion criteria, medical/dermatological history, Fitzpatrick Skin Type assessment, and concomitant medications and therapies will be reviewed to determine subject eligibility. If required, the subject will be given adequate washout to discontinue prohibited medications or treatments as specified by the protocol.
 
Once washout has been completed, the following assessments will be performed. A brief physical exam including vital signs and UPT (if applicable) will be performed. The Treatment Area will be defined as a contiguous 25 cm² area on the face or scalp containing at least four, but no more than eight AKs. All AK lesions, independent of size, in the Treatment Area will be counted and evaluated for size. Local skin reactions (LSRs) will be assessed. Subject will be randomized (1:1:1) to treatment and instructed how to apply the test article to the Treatment Area via demonstration using non-medicated samples. Test article (with instructions) and subject diary will be dispensed to the subject. The subject will be instructed to apply the test article to the designated Treatment Area once per day for three days (washing their hands after each application) and to record the date and time of applications in the subject diary. After each application the test article will be washed off after six hours. The subject will be scheduled for follow-up at Visit 2/Day 4.
 
Visits 2, 3, and 4 (Follow-Up): Days 4, 8, and 15. The subject will return to the clinic and will be queried for any changes in health status and concomitant medications and therapies. The test article and subject diary will be collected at Day 4. LSRs will be assessed. The subject will be scheduled for the next follow-up visit.
 
Visit 5 (Follow-Up): Day 29. The subject will return to the clinic and will be queried for any changes in health status and concomitant medications and therapies. AK lesions, new and pre-existing (i.e., Baseline), will be counted. LSRs will be assessed. The subject will be scheduled for Visit 6/Day 57.
 
Visit 6 (End of Study [EOS]): Day 57. The subject will return to the clinic

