Sample Size Calculations	
Based on conservative assumptions of a complete lesion clearance rate of 50% for both active treatments and a rate of no more than 15% for the vehicle treatment, 480
 

Statistical Methods	
All statistical processing will be performed using SAS[®]. Summary tables (descriptive statistics and/or frequency tables) will be provided for baseline variables, efficacy variables, and safety variables. Continuous variables will be described by descriptive statistics (n, mean, median, standard deviation, minimum, and maximum). Frequency counts and percentage of subjects within each category will be provided for categorical data. Summaries will be provided for each treatment group.
 
Study Populations: The Safety population will include all randomized subjects who received the test article. The mITT population will include all randomized subjects who applied at least one dose of test article. The PP population will include all randomized subjects who met all the inclusion/exclusion criteria, were compliant with the assigned test articles (applied all three doses of the test article and no other evidence of material dosing noncompliance), completed the study within the designated visit window (± 2 days), and had no protocol violations that would affect treatment evaluation. Subjects who discontinued early from the study due to lack of treatment effect or who worsen and require alternate or supplemental therapy will be included in the PP population as treatment failures (non-responders). Subjects discontinued prematurely for other reasons will be excluded from the PP population, but included in the mITT population.
 
Efficacy Analyses: The efficacy analyses will be conducted on the mITT and PP populations. Last-observation-carried-forward (LOCF) will be used to impute missing values for efficacy variables in the mITT population.
 
Bioequivalence. Evaluations in the PP population will be considered primary. The 90% Wald's confidence interval with Yate's continuity correction will be constructed on the difference between the proportion of subjects with complete (100%) lesion clearance in the Test and Reference treatments to evaluate bioequivalence of the two active treatments. If the 90% confidence intervals on the difference between the proportion of subjects with complete lesion clearance in the Test and Reference treatments are contained within the interval -0.20 to +0.20, then the Test and Reference products will be considered to be therapeutically equivalent.
 
Superiority. To determine study sensitivity, two-sided, Fisher's exact test with an alpha of 0.05 will be used to evaluate the superiority of each active treatment over the vehicle for the proportion of subjects with complete (100%) lesion clearance using mITT population and LOCF. This test will be repeated on the PP population.
 
Safety Analyses: The analysis of safety will be conducted on the Safety population.
 
Dosing Compliance Descriptive statistics will be used to summarize test article compliance for the mITT and PP populations. Measures of test article compliance will include the total number of applications as determined from the data recorded in the subject diaries. Compliant subjects will be defined as those

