17. STATISTICAL CONSIDERATIONS

17.1 Sample Size

Based on conservative assumptions of a complete lesion clearance rate of 50% for both active treatments and a rate of no more than 15% for the vehicle treatment, 480 modified

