17.3.1 Efficacy Analyses

The efficacy analyses will be conducted on the mITT and PP populations. Last-observation-carried-forward (LOCF) will be used to impute missing values for efficacy variables in the mITT population.

Bioequivalence. Evaluations in the PP population will be considered primary. The 90% Wald's confidence interval with Yate's continuity correction will be constructed on the difference between the proportion of subjects with complete (100%) lesion clearance in the Test and Reference treatments to evaluate the bioequivalence of the two active treatments. If the 90% confidence intervals on the difference between the proportion of subjects with complete lesion clearance in the Test and Reference treatments are contained within the interval -0.20 to +0.20, and each of these proportions is greater than, and statistically different ($p < 0.05$) from, the Placebo proportion, then the Test and Reference products will be considered to be therapeutically equivalent.

Superiority. To determine study sensitivity, two-sided, Fisher's exact test with an alpha of 0.05 will be used to evaluate the superiority of each active treatment over the vehicle for the proportion of subjects with complete (100%) lesion clearance using mITT population and LOCF. This test will be repeated on the PP population.

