3 STUDY OBJECTIVES AND ENDPOINTS

The objectives of the study are to evaluate the safety and therapeutic equivalence of generic ingenol mebutate gel, 0.015% to Picato gel, 0.015% by establishing the therapeutic comparability of the two active products and the superiority of the two active products over the vehicle gel in the treatment of actinic keratoses (AK) on the face and scalp.

Primary efficacy endpoint is the proportion of subjects in each treatment group with complete clearance of AK lesions at Visit 6/Day 57. Complete (100%) clearance is defined as having no (zero) clinically visible AK lesions in the Treatment Area.

Safety endpoints will include assessment of the severity and frequency of Adverse Events (AEs) and Local Skin Reactions (LSRs).

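### Protocol 17.3.1 lets equivalence be concluded only if both actives beat Placebo; the synopsis rule drops that condition, and SAP 8.6.1 gives no consequence if a vehicle test fails

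*SAP*

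**What the plan says.** - **Protocol 17.3.1 (Efficacy Analyses)** sets two conditions for therapeutic equivalence: the 90% interval for Test minus Reference lies within ±0.20, and "each of these proportions is greater than, and statistically different" (p<0.05) from Placebo.
- **Protocol Synopsis (Statistical Methods)** gives almost the same sentence with one condition. If the interval limits "are contained within the interval -0.20 to +0.20, then the Test and Reference products will be considered to be therapeutically equivalent". Superiority follows as a separate paragraph on study sensitivity.
- **SAP 8.6.1 (Primary Efficacy Analyses)** states the null for Test minus Reference at ±0.2, tests it with the 90% interval in the PP population, and adds: "Rejection of the null hypothesis supports the conclusion of equivalence of the test and reference treatments". The vehicle comparisons come next, with the purpose "To establish that the study is sufficiently sensitive to detect difference between treatments". Nothing says what happens to the equivalence conclusion if one or both fail.
- **The objectives** (Protocol 3 and Synopsis, SAP 3) name both aims: "therapeutic comparability of the two active products and the superiority of the two active products over the vehicle gel".

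Two smaller differences affect the same rule. The Placebo condition in 17.3.1 names no population: it sits in the paragraph that makes PP primary, while the superiority paragraphs of both documents use mITT first and repeat on PP. The superiority test is Fisher's exact in the protocol, and a continuity-corrected chi-square with Fisher as fallback for small expected counts in the SAP.

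**The concern.** A narrow interval around Test minus Reference shows that the two gels performed alike in this study. It does not show that either worked. The vehicle arm is there to supply that evidence. The interval condition also becomes easier to meet as clearance falls, because a binomial variance is smaller at 15% than at 50%. A study with poor application, lesion miscounting or an ineffective batch would therefore tend to pass on the interval alone.

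If a vehicle test failed, 17.3.1 would bar an equivalence conclusion, while the synopsis and SAP wording would leave it open. The choice of governing text would then be made after unblinding. The weakness is one of assay sensitivity; the type I error of the Test-Reference test is not inflated.

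**Working it through.** **Inputs from the documents**
- Margin ±0.20; 90% Wald interval with Yates correction (Protocol 17.3.1, SAP 8.6.1).
- Superiority: two-sided, alpha 0.05, corrected chi-square, or Fisher's exact if an expected count is below 5 (SAP 8.6.1).
- Planning rates: "a complete lesion clearance rate of 50% for both active treatments and a rate of no more than 15% for the vehicle treatment" (Protocol 17.1).
- About 480 subjects (Protocol 4). Allocation: "Subject will be randomized (1:1:1) to treatment" (Synopsis, Study Procedures), giving 480/3 = 160 per arm.

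**Assumptions**
- The allowance for losses is not visible, so losses of 0%, 15% and 30% are used: 160, 160 × 0.85 = 136, and 160 × 0.70 = 112 per arm.
- The same n serves the interval (PP) and the vehicle tests (mITT).

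The target power behind 480 is not visible either, so that figure cannot be formally reproduced. It is plausible: the exact power of the interval criterion at 50/50 is 93.5% with 160 per arm.

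**Formulas**
- Interval: (pT − pR) ± {1.645 × √[pT(1 − pT)/nT + pR(1 − pR)/nR] + ½(1/nT + 1/nR)}.
- Corrected chi-square for counts x and v with n per arm: χ² = 2n(|x(n − v) − v(n − x)| − n)² / [n²(x + v)(2n − x − v)], compared with 3.84.

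**One outcome by hand.** Take Test 24/160 (15%), Reference 40/160 (25%), vehicle 24/160 (15%).
- Standard error: √(0.15 × 0.85/160 + 0.25 × 0.75/160) = 0.0444.
- Half-width: 1.645 × 0.0444 + 1/160 = 0.0730 + 0.0063 = 0.0792.
- Interval: −0.10 ± 0.0792 = −0.179 to −0.021, inside ±0.20.
- Reference v vehicle: χ² = 320 × (|40 × 136 − 24 × 120| − 160)² / (160² × 64 × 256) = 4.39, above 3.84, so it passes.
- Test v vehicle: identical counts, so it fails.

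The synopsis and SAP wording would allow equivalence for a Test gel that did exactly as well as vehicle. Under 17.3.1 it could not be concluded.

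**Probability of passing.** Exact binomial enumeration over all three arms; the 17.3.1 rule also requires both actives to beat vehicle.

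| True rates T/R/V (%) | Rule | 160 per arm | 136 per arm | 112 per arm |
|---|---|---|---|---|
| 15/15/15 | Interval only | 99.8% | 99.4% | 98.1% |
| | 17.3.1 | 0.3% | 0.3% | 0.3% |
| 15/25/15 | Interval only | 68.3% | 61.0% | 53.5% |
| | 17.3.1 | 1.5% | 1.4% | 1.2% |
| 50/50/15 | Interval only | 93.5% | 87.1% | 79.6% |
| | 17.3.1 | 93.5% | 87.1% | 79.6% |

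Between these extremes, at 160 per arm (interval only v 17.3.1): 40/40/15, 94.1% v 94.0%; 30/30/15, 96.8% v 78.1%; 25/25/15, 98.2% v 39.2%.

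Using Fisher's exact test throughout moves the 17.3.1 probability by at most 0.7 percentage points in these scenarios, and not at all at 50/50/15. The difference in test is therefore a matter of consistency more than of size.

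**The case against.** The strongest reply is that the rule already exists. Section 17.3.1 is the protocol's full statistical section, the SAP says it was written from that protocol version, and it announces no departure. The objectives pair comparability with superiority. The SAP sentence says only that rejection supports equivalence, and both vehicle tests sit under the primary-analysis heading, so a failure would be reported beside the interval.

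Much of this stands. The intent is clear, the SAP wording is softer than the synopsis wording, and this is a rule carried over incompletely, not a trial without one. But an objective is not a decision rule, a stated purpose for a test is not a consequence of failing it, and neither document says which text governs. Redaction does not explain the gap: the synopsis and 17.3.1 sentences are both complete, and SAP 8.6.1 shows no missing text at this point.

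A second reply is that the large gaps need unfavourable truths. That is correct. In the 15/25/15 case the true difference of 10 points is inside the margin, so passing the interval is the right answer to the Test-Reference question. What goes wrong is reading that answer as therapeutic equivalence when Test is no better than vehicle.

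**Conclusion.** The concern holds. The synopsis and SAP 8.6.1, followed literally, allow an equivalence conclusion that Protocol 17.3.1 forbids.

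The table contrasts wordings; it does not give an error rate for the trial. The rules agree at the planned rates and almost agree at 40/40/15. They part as active clearance falls towards vehicle, in the extreme 99.8% v 0.3%. The figures rest on 1:1:1 allocation, assumed losses of 0% to 30%, and one n for all tests. A larger mITT than PP population would raise the 17.3.1 probabilities for the vehicle comparisons somewhat wherever an active truly beats vehicle, and would leave the contrast in place.

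The conflict concerns the primary conclusion and should be settled before unblinding.

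**What to change.** Put the 17.3.1 rule into the synopsis and SAP 8.6.1 with a linking statement such as:

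> Therapeutic equivalence will be concluded only if (a) the 90% confidence interval for Test minus Reference in the PP population lies within −0.20 to +0.20, and (b) in the mITT population Test and Reference each have a higher success proportion than vehicle with two-sided p<0.05. If (b) fails for either active, equivalence is not concluded, whatever the result of (a). Superiority results in the PP population are supportive.

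The existing SAP sentence on rejecting the null can stay if it refers to this rule. Name the population in the 17.3.1 Placebo clause. The mITT choice above follows the superiority paragraphs of both documents, but 17.3.1 leaves it open, so the sponsor should confirm it. Name one superiority test in both documents.

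**Cost.** A text change plus that one confirmation. No alpha adjustment is needed, because every condition must be met. No power is lost at 50/50/15. Against the interval-only wording, power falls if the true active effect is small (98.2% to 39.2% at 25/25/15, 160 per arm). Against 17.3.1 as written there is no added cost, since it already requires superiority.
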